#### **6.4.5. Secondary Efficacy Analyses at Month 18 and End of Study**

The secondary efficacy analysis will be conducted using the ITT Population. The secondary endpoints for the Month 18 Interim Analysis are:

##### Key Secondary Endpoint:

- Percentage of subjects with improvement of fibrosis by at least 1 stage AND/OR resolution of NASH, without worsening of either

[figure not shown]
##### Secondary Endpoints:

[figure not shown]
- Percentage of subjects with no worsening of fibrosis AND no worsening of NASH
- Percentage of subjects with progression to cirrhosis
- Percentage of subjects with improvement of fibrosis by at least 2 stages
- Percentage of subjects with improvement of each key histological feature of NASH by at least 1 point (steatosis, lobular inflammation, and hepatocellular ballooning)
- Percentage of subjects with improvement of NAS by at least 2 points with no worsening of fibrosis
- Percentage of subjects with improvement of fibrosis and resolution of NASH as a composite endpoint and as defined by both endpoints being met in the same subject
- Percentage of subjects with resolution of fibrosis.

[figure not shown]
The analyses will compare placebo and each OCA dose separately (10 mg and 25 mg), using a CMH test stratified by the randomization strata (diabetes at enrollment [yes/no] and use of TZDs or vitamin E at baseline [yes/no]).

These analyses will also be conducted using the mITT, PP and Full Efficacy Analysis Populations.

At the End of Study Analysis, all Month 18 histological endpoints will be analyzed.

[figure not shown]

S

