9.9.7. Month 18 Procedures

Note: Month 18 liver biopsy was performed for subjects who were enrolled in the interim analysis cohort. Subjects randomized on or after 16 Jul 2017 who have not had a Month 18 biopsy are no longer required to have a biopsy at this visit unless progression to cirrhosis is suspected.

[figure not shown]
Month 18 Visit procedures for all subjects are as follows:

- Verify that the subject has fasted for at least 8 hours
 - Record fasting status in the source and CRF
 - If the subject reports having eaten within 8 hours, document accordingly in the source and CRF and remind the subject that fasting is required before all study visits after screening.
- Perform a physical examination
- Perform a standard 12-lead ECG
- [redacted] and vital signs (body temperature, sitting heart rate, respiratory rate, and sitting blood pressure)
- [redacted]
- Determine alcohol consumption (AUDIT questionnaire), smoking habits, and caffeine consumption
- [redacted]

- Perform hepatobiliary ultrasound for [REDACTED] screening and for gallbladder assessment
- Assess and record AEs
- Review and record concomitant medications

- Serum chemistry, hematology, and coagulation
- Thyroid hormones
- Free fatty acids
- Insulin, c-peptide, and HOMA-IR
- Glucose and HbA1c
- Apoptosis markers (CK-18 M30 and CK-18 M65)
- Noninvasive assessments of liver fibrosis (ELF, Fibrotest/Fibrosure)
- Inflammation marker (hs-CRP)
- [REDACTED]
- Educate subjects about signs and symptoms of potential hepatic injury or decompensation (as needed, per Investigator's discretion)
- Evaluate signs and symptoms of potential hepatic injury or decompensation and assess subjects per Potential DILI Management and Progression to Cirrhosis Algorithms
 - In subjects who progress to cirrhosis and have a CP score <7, 1 PK blood sample will be obtained at the next scheduled visit prior to dose adjustment. Subjects who discontinue investigational product due to progression to cirrhosis and Child Pugh score ≥ 7 or due to hepatic injury, will provide a PK blood sample within 7 days from dose interruption or discontinuation. The time of the last dose of investigational product prior to the PK blood sample will be reported.
- Calculations will be performed by the Sponsor or designee for
 - MELD score

- Obtain urine sample for urinalysis
- Perform a urine-based β -hCG pregnancy test for females of childbearing potential
- Provide lifestyle modification counseling

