16.6.3. Responder Endpoints

For the analyses of the primary and key secondary histological efficacy endpoints, in which subjects are classified as either a responder or a non-responder (binary outcome), any subject who does not provide any assessment at the specified timepoint and after baseline for the defining of response will be considered to be a non-responder. That is, for the percentage of responders, the subject will be included in the denominator and will not contribute to the numerator. Subjects who early terminate before Month 18, biopsy results at the time of early termination, if available, will be included in Month 18 histological endpoints analyses.

A completer analysis will also be conducted, excluding those subjects who do not provide an assessment at the specified timepoint for the defining of response. That is, for the percentage of responders, the subject will not be included in the numerator or the denominator.

Additional sensitivity analysis will be described in the SAP.

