#### 3.4.1. Month 18 Interim Analysis Populations

The Month 18 Interim Analysis data cutoff date (DCO) has been pre-specified to include all subjects' data for visits (scheduled or unscheduled) occurring on or before that date. The Interim Analysis Cohort (original Month 18 IA Cohort) will include all randomized subjects who received at least one dose of investigational product by the DCO. The original Month 18 IA Cohort will include all fibrosis stages (stages 1, 2 and 3).

The following analysis populations will be evaluated and used for presentation and analysis of Month 18 Interim Analysis data:

- The Safety Population will include the entire IA Cohort, all fibrosis stages (stages 1, 2 and 3), who received at least 1 dose of investigational product (OCA or placebo) by the DCO. Treatment assignment will be based on the treatment actually received.
- The Full Efficacy Analysis Population will include all original Month 18 IA Cohort subjects, randomized by 15 July 2017, including all fibrosis stages (stages 1, 2, and 3), who received at least 1 dose of investigational product. The selected randomization cut-off date ensures an adequate sample size for the efficacy assessment, considering that subjects randomized by 15 July 2017 would have reached their Month 18 biopsy visit by December 2018 based on 72 week treatment period. Treatment assignment will be based on the randomized treatment.
- The Intent-to-Treat (ITT) Population will include a subset of the Full Efficacy Analysis Population, limited to those subjects with fibrosis stage 2 or stage 3. Treatment assignment will be based on the randomized treatment. The ITT Population will be the primary efficacy analysis population.
- The modified ITT (mITT) Population will include all subjects from the ITT Population, with the exception of a subgroup of subjects who discontinued treatment (before the Month 18 Visit and without an end of treatment biopsy) between 13 Sep 2017 and 19 Dec 2017 for the following reasons: withdrawal of consent, lost to follow-up, and due to other reasons. The observed increase in the number of discontinuations during the above-mentioned period was an unintended consequence of 1) safety communications eliciting concern from subjects and physicians and 2) increased subject and site burden due to the safety amendment. Treatment assignment will be based on the randomized treatment. The mITT population will serve as a supportive analysis population.

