### **3.4.2. End of Study Analysis Populations**

- The Safety Population will include all randomized subjects who received at least 1 dose of investigational product (OCA or placebo). Treatment assignment will be based on the treatment actually received.
- The Full Efficacy Analysis Population will include all randomized subjects, all fibrosis stages (stages 1, 2 and 3), who received at least 1 dose of investigational product. Treatment assignment will be based on the randomized treatment.
- The Intent-to-Treat (ITT) Population will be a subset of the Full Efficacy Analysis Population, limited to those subjects with fibrosis stage 2 or stage 3. Treatment assignment will be based on the randomized treatment. The ITT Population will be the primary efficacy analysis population. The Per Protocol (PP) Population will include all subjects from the ITT Population who did not have any major protocol deviation ([Section 5.5](#)) that could potentially affect the efficacy conclusions and at least 80% compliance with investigational product ([Section 10.1](#)). Treatment assignment will be based on the randomized treatment.
- The PK Population will include all subjects who received OCA and have at least one confirmed fasted analyzable sample. Subjects must have been fasting for approximately 8 hours before the visit and must not have any major protocol deviations that potentially affect exposure levels. The PK Population will be used for OCA PK.

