Panel A of 3 pathologists will read images of slides stained with H&E to characterize NAS (ballooning, inflammation, steatosis) score and Panel B pathologists will read images of slides stained with Trichrome to characterize NAS CRN fibrosis score. The endpoint regarding the improvement or worsening of fibrosis stage and NASH will be derived based on the results from the consensus values at baseline and any post-baseline liver biopsy collection.

For the analyses of histological efficacy endpoints, in which subjects are classified as either responders or non-responders (binary outcome), any subject who discontinues from the study prior to the Month 18 biopsy Visit and does not have a post-baseline biopsy assessment will be considered a non-responder. Biopsies collected for subjects who discontinued treatment before the Month 18 visit will be included in the Month 18 Interim Analysis of histological endpoints regardless of the timing of the biopsy.

Similar conventions and statistical methodologies will be used for analyses of other exploratory histological-based responder analyses. Responder endpoint analyses will be carried out for the primary and secondary endpoints using the ITT, mITT, Full Efficacy Analysis Population and PP Populations.

A complete summary and description of the analysis plan and populations for histological data based on the consensus method can be found in SAP Addendum V2 (dated 25 Apr 2022).

[figure not shown]

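### Month 18 histology is to be analysed again at End of Study in an ITT with no randomisation cut, although later subjects no longer needed the Month 18 biopsy, and the protocol and SAP missing-data rules treat them differently

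*SAP*

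**What the plan says.** **Analysis and population.** SAP 6.4.5 covers secondary efficacy at both Month 18 and End of Study. It says "The secondary efficacy analysis will be conducted using the ITT Population", lists the histology endpoints, and closes with "At the End of Study Analysis, all Month 18 histological endpoints will be analyzed". SAP 3.4.2 defines the End of Study ITT as a "subset of the Full Efficacy Analysis Population, limited to those subjects with fibrosis stage 2 or stage 3". Neither that section nor SAP Table 3 puts a randomisation date on it. The 15 July 2017 cut appears only among the Month 18 populations in SAP 3.4.1, because "subjects randomized by 15 July 2017 would have reached their Month 18 biopsy visit by December 2018 based on 72 week treatment period".

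**Biopsy requirement.** Protocol 9.9.7 says: "Subjects randomized on or after 16 Jul 2017 who have not had a Month 18 biopsy are no longer required to have a biopsy" at that visit, with an exception where cirrhosis is suspected. SAP 6.2.2 still describes the Month 18 biopsy as a protocol requirement and does not mention this release.

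**Missing data.** Protocol 16.6.3, for primary and key secondary histology, makes a non-responder of "any subject who does not provide any assessment at the specified timepoint and after baseline for the defining of response" and keeps that subject in the denominator. It adds a completer analysis. SAP 6.2.2 makes a non-responder only of "any subject who discontinues from the study prior to the Month 18 biopsy Visit and does not have a post-baseline biopsy assessment". SAP Section 4 and Appendix A otherwise base percentages on non-missing data by default.

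**Another description of End of Study histology.** SAP 2.3.2.2.1 lists largely the same endpoints, but derives them from every biopsy after baseline and names no timepoint.

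**The concern.** A Month 18 response can be observed only in subjects who have a Month 18 biopsy. At End of Study the denominator includes a cohort that was released from that biopsy by calendar date. For this cohort a missing value mostly reflects the schedule. It says little about treatment failure.

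The two missing-data rules then give different answers. The protocol rule counts a biopsy that was not required as non-response, which pulls all response rates and their differences toward zero. The SAP rule keeps the later cohort's early leavers as failures and gives no value to those who stay, so membership of the denominator depends on an event after randomisation.

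There is also selection. In the later cohort the Month 18 biopsy is required only when cirrhosis is suspected, so biopsies in the Week 60 to 96 window would tend to come from suspected progressors. That matters most for the progression-to-cirrhosis endpoint. At stake are the reported Month 18 effect sizes at End of Study and whether they can be compared with the interim results.

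**Working it through.** **1. The plan's own date.** 15 July 2017 + 72 weeks (504 days) = 1 December 2018. This agrees with SAP 3.4.1, so the SAP's cut and the release date in Protocol 9.9.7 are the two sides of one boundary.

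**2. Inputs.** N = 2085 planned stage 2/3 subjects, 695 per arm at 1:1:1 (Protocol 7.2, SAP 2.2.1). The minimum interim cohort is 750 (SAP 2.2.1). The documents do not give E, the number of stage 2/3 subjects randomised by 15 July 2017. I take 750, 1000 and 1250 as assumptions. Response rates of 15% v 25% are also assumed.

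**3. Protocol rule.** Suppose everyone in the later cohort lacks a Month 18 biopsy and counts as a non-responder.
- Later-cohort share = 1 − E/N
- Reported rate = true rate × E/N
- Reported difference = true difference × E/N

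| E | E/N | Later cohort | 15% v 25% reads as | 10 points becomes | Power, full ITT | Power, randomised by the cut |
|---|---|---|---|---|---|---|
| 750 | 0.36 | 64% | 5.4% v 9.0% | 3.6 | 74% | 80% |
| 1000 | 0.48 | 52% | 7.2% v 12.0% | 4.8 | 86% | 90% |
| 1250 | 0.60 | 40% | 9.0% v 15.0% | 6.0 | 93% | 95% |

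Power is at a two-sided 0.05, for illustration only. SAP 2.2.1 also gives about 2480 randomised. If 285 of these are stage 1 (assumption), N = 2195 and the later-cohort shares are 66%, 54% and 43%. The loss of power is modest; the main damage is to the estimate. These are upper figures for each E, because any later-cohort subject who did have the biopsy reduces the effect.

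**4. SAP rule.** Let d be the proportion who leave the study before the visit with no biopsy after baseline. With E = 750 there are 250 per arm by the cut and 695 − 250 = 445 later. Later-cohort subjects who stay have no value and drop out under the non-missing default.
- Reported rate = responders / (250 + 445 × d)

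Take 15% response among those biopsied in both arms, and d = 25% v 12%. All of these are assumptions.
- Responders: 250 × 0.75 × 0.15 = 28.1; 250 × 0.88 × 0.15 = 33.0.
- Subjects randomised by the cut: 28.1/250 = 11.2%; 33.0/250 = 13.2%. Gap 2.0 points.
- Full ITT: 28.1/361.25 = 7.8%; 33.0/303.4 = 10.9%. Gap 3.1 points.

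Only about 1.1 points of the gap come from including the later cohort. The other 2.0 are ordinary non-responder imputation. The sign follows from the assumed drop-out and would reverse if the drop-out rates were swapped.

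**The case against.** The strongest reply is that SAP 6.4.5 may only carry the Month 18 endpoint list forward to End of Study. SAP 2.3.2.2.1 supports this: with every biopsy after baseline in use, Month 48 and end-of-treatment biopsies would count. SAP 6.4.5 also names the mITT, which Table 3 marks as not applicable at End of Study, so some of its population text was clearly written for the interim analysis. This reading is possible and stands as an ambiguity. It does not settle the matter, because SAP 2.3.2.2.1 does not say which biopsy counts when a subject has several, and it would mix Month 18 and Month 48 results according to enrolment date.

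Further limits stand:
- Protocol 16.6.3 covers only primary and key secondary histology, uses early-termination biopsies, and adds a completer analysis.
- The release in Protocol 9.9.7 is conditional, so some later subjects may have Month 18 biopsies. It would be wrong to say that the biopsy was never scheduled for any of them.
- 750 is a minimum, so 64% is the upper end of the range shown for N = 2085.
- SAP 6.2.3 and SAP Addendum V2.0 are not available here, and nothing is inferred from what they may contain.

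A reader might infer that OCA 25 mg would be penalised. The documents do not support this. They give no drop-out by arm for this purpose, subjects who stop drug are expected to stay on study, and the date cut is common to all arms.

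**Conclusion.** The point holds as an unresolved population and missing-data rule for secondary histology at End of Study. The ITT there has no date cut, the Month 18 biopsy was lifted for later subjects, SAP 6.2.2 does not acknowledge this, and no visible text limits the denominator.

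Under the protocol rule, 40% to 64% of the stage 2/3 population belongs to the later cohort and a 10-point difference would read as 6.0 to 3.6 points. This assumes 1250 to 750 of 2085 randomised by the cut and no Month 18 biopsies after it. Under the SAP rule no size can be derived from the documents. What can be said is that the denominator depends on discontinuation, with no established direction between arms.

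The tempting wider claim, that the plan turns all unrequired biopsies into failures, is not supported. It follows from the protocol rule for the endpoints that rule covers. Under the SAP rule it applies only to later-cohort subjects who left the study before Month 18 with no biopsy after baseline. SAP 6.3.2 and Table 4 allocate End of Study alpha only to the clinical composite, so the consequence concerns estimation and interpretation. It should be corrected, but it does not threaten the primary conclusion.

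**What to change.** Amend the SAP as follows:
- **Population.** In 6.4.5, analyse the Month 18 endpoints at End of Study in ITT subjects randomised by 15 July 2017, the cut the SAP already uses. Show any Month 18 biopsies from the later cohort as supportive.
- **Timepoint.** Reconcile 6.4.5 with 2.3.2.2.1. Analyse Month 48 and other biopsies after baseline separately by timepoint, and state which biopsy counts when a subject has several.
- **Missing data.** Use one rule, consistent with Protocol 16.6.3, that imputes non-response only where the biopsy was required at that timepoint.
- **Consistency.** Bring the statement in SAP 6.2.2 about the Month 18 biopsy into line with Protocol 9.9.7.

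The cost is wording and a smaller denominator for secondary endpoints that carry no allocated End of Study alpha. In the illustration under the protocol rule, the restricted analysis has slightly more power than the full ITT despite its smaller size.

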#### **6.4.6.10. Change from Baseline in MELD**

MELD score is a scoring system for assessing the severity of chronic liver disease. Higher scores on MELD indicate worse disease severity.

MELD during treatment will be compared to baseline values to determine if there was an increase in MELD score, and this information will be summarized by treatment group and visit. MELD score, change and percentage change from baseline values will be summarized and analyzed as described in the General Statistical Methods ([Section 4](#)).

Individual factors contributing to the MELD score will be presented in a listing.

#### **6.4.7. End of Study Time to Event Analyses**

In addition to the primary analysis (Section 6.4.4.2) and secondary analyses (Section 6.4.5) and exploratory analyses (Section 6.4.6), the following analyses will be performed at the End of Study.

##### **6.4.7.1. Time to Each Component of the Clinical Outcome Endpoint**

[figure not shown]
[figure not shown]
Time to each of the following components of the clinical outcome endpoint and time to HCC will be analyzed by treatment group using ITT and Full Efficacy Analysis Populations:

[figure not shown]
- Death: date of death
- Liver transplant: date of first liver transplant
- MELD score  $\geq 15$ : date of first occurrence of MELD  $\geq 15$
- Hospitalization (as defined by an inpatient stay of 24 hours or greater) for new onset or recurrence of: variceal bleed, encephalopathy (as defined by a West Haven grade  $\geq 2$ ), spontaneous bacterial peritonitis (confirmed by diagnostic paracentesis): date of earliest hospitalization admission.
- Ascites secondary to cirrhosis and requiring medical intervention: date of earliest ascites start date as an adverse event that required medical intervention.
- Histological progression to cirrhosis: date of biopsy

[figure not shown]
Only adjudicated events (and biopsy confirmed progression to cirrhosis) will be included in the analyses. The time to event of each of the components of the clinical outcome endpoint are defined as follows:

[figure not shown]
- Time to death (all-cause), first MELD score  $\geq 15$  and first liver transplant will be calculated in days as the date of the event minus the date of randomization plus 1. Subjects who do not experience an event will be censored at the date of last contact.
- Time to the first occurrence of onset of ascites (secondary to cirrhosis and requiring medical intervention), will be calculated in days as the first time for onset of the ascites minus the date of randomization plus 1.
- Time from randomization to the date of biopsy confirming histological progression to cirrhosis will be calculated in days as the date of the diagnosis minus the date of randomization plus 1. Subjects who do not experience an event will be censored at the date of last contact.
- Time to the first occurrence of hospitalization for new onset or recurrence of variceal bleed, encephalopathy, spontaneous bacterial peritonitis will be calculated in days as the first hospitalization admission date/time for new onset or recurrence of the event minus the date of randomization plus 1. The duration between the hospitalization admission date/time and discharge date/time (discharge date/time – admission date/time) must be greater than or equal to 24 hours (1 day). Subjects who do not experience an event will be censored at the date of last contact.

[figure not shown]
KM estimates of the time-to-event will be tabulated and graphed by treatment group. The tabulation will include the KM estimate of the medians and corresponding 95% CIs, if the medians can be estimated. The number and percent of subjects censored and with events will be presented. All summaries of incidence will include the associated exact binomial 95% confidence Interval (CI). Listing of adjudicated events, including progression to cirrhosis will be provided. At the Month 18 Interim Analysis, a listing of adjudicated events will be prepared by DMC vendor without unblinding the Sponsor as described in the DAP.

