7. INVESTIGATIONAL PLAN

7.1. Overall Study Design

This Phase 3, double-blind, randomized, long-term, placebo-controlled, multicenter international study will evaluate the effect of OCA on histological improvements in NASH, all-cause mortality, and liver-related clinical outcomes. The study will enroll approximately 2370 subjects with NASH. The population will comprise approximately 2085 subjects with biopsy-confirmed, noncirrhotic NASH and evidence of stage 2 or stage 3 liver fibrosis, including

approximately 60% with fibrosis stage 3 and approximately 40% with fibrosis stage 2; and an additional cohort of approximately 285 subjects with stage 1 fibrosis with at least 1 accompanying comorbidity to gather information on the safety of OCA and progression of liver disease in this population.

A planned Interim Analysis is to be performed when a minimum of 750 randomized subjects (the first sequential) with fibrosis stage 2 or stage 3 would have reached their actual/planned Month 18 Visit. For the purpose of determining the timing of the Month 18 Interim Analysis, subjects that discontinue before their Month 18 visit are considered to have reached their Month 18 Visit and will be part of the Month 18 Interim Analysis cohort. The cutoff for the Month 18 Interim Analysis cohort database lock will be defined in the SAP. The study will be continued in a blinded fashion, and subjects will be followed for clinical outcomes to confirm clinical benefit. Final analysis will evaluate the effect of OCA on mortality and liver-related clinical outcomes and long-term safety of OCA after the accrual of approximately 291 adjudicated clinical outcomes composite events combined in the OCA 25 mg and placebo groups for subjects with fibrosis stage 2 or stage 3 (projected to take approximately 10 years in total). Subjects are expected to have a minimum follow-up time of approximately 4 years.

[figure not shown]

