**Table 1: Estimands for Clinical Composite Outcome**

Estimands	Population	Endpoint	Intercurrent Events	Strategy for IEs	Population-Level Summary
Primary	ITT	Time to the first occurrence of the specific clinical composite outcomes	Investigational Product discontinuation or interruption or dose adjustment	Treatment Policy	Difference in time to the first occurrence of the clinical outcome events between OCA and placebo at end of study
	Same as above	Same as above	Study discontinuation due to various reasons or death, or withdrawal or lost to follow up	While on treatment policy	Difference in time to first occurrence of the events including death, and clinical outcomes before study discontinuation, withdrawal or lost to follow. Otherwise, it will be censored.

IE=intercurrent events; ITT=intent-to-treat; OCA=obeticholic acid

[figure not shown]
[figure not shown]

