Time-to-event data will be summarized using Kaplan-Meier (KM) methodology using 25th, 50th (median), and 75th percentiles with associated 2-sided 95% CIs, as well as the percentage of censored observations. KM estimates will be plotted as a “survival curve” for each treatment group, with the number at risk identified. In addition, time-to-event data will be summarized with descriptive statistics for those subjects with an event. Subjects who do not experience an event will be censored. Subjects who do not experience an event will be censored at the date of last contact for clinical outcome endpoints and will be censored at the earliest date of last dose date+30 days, end of study, death date or date cut-off date for treatment-emergent adverse events (TEAEs). The censor date for time to resolution events will be the earliest date of end of study, death date or date cut-off date.

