### **Last Contact Date:**

Last contact date for time-to-event analysis is calculated as follows:

- Ongoing Subjects (including subjects on-treatment and subjects that discontinued treatment but on-study): DCO date
- Subjects that discontinued study: The date of study discontinuation
- Subjects lost to follow up: The latest of last assessment, last visit, and last dose date

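### The Kaplan-Meier displays for the non-fatal components do not say how death is handled; if death is censored, the curves read as incidence run modestly too high, mainly in the late tail

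*SAP*

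**What the plan says.** SAP Section 6.4.7.1 analyses each component of the clinical outcome endpoint separately, by treatment group, in the ITT and Full Efficacy Analysis Populations. The displays are Kaplan-Meier: "KM estimates of the time-to-event will be tabulated and graphed by treatment group", with medians where they can be estimated. The censoring rule for most components is "Subjects who do not experience an event will be censored at the date of last contact". The ascites bullet has no rule of its own, but SAP Section 4 covers it, since subjects without an event are "censored at the date of last contact for clinical outcome endpoints".

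The same section reports numbers and percentages with events and adds: "All summaries of incidence will include the associated exact binomial 95% confidence Interval (CI").

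The last-contact date is defined in SAP Appendix A. Ongoing subjects take the data cutoff. For withdrawals the entry is "Subjects that discontinued study: The date of study discontinuation". Subjects lost to follow-up take the latest of last assessment, visit or dose. Death is not in the list. The nearest guide is SAP Table 1, where one row of intercurrent events reads "Study discontinuation due to various reasons or death, or withdrawal or lost to follow up". By contrast, SAP Section 4 names the death date explicitly as a censoring date for treatment-emergent adverse events.

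Protocol Section 7.1 gives the time scale. The study is "projected to take approximately 10 years in total", and "Subjects are expected to have a minimum follow-up time of approximately 4 years".

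**The concern.** A subject who dies without a transplant, ascites or biopsy-proven cirrhosis can no longer have that event. Kaplan-Meier with the death censored treats that subject as someone who would have gone on to have the event at the same rate as those still followed. The complement of the curve then describes a setting in which nobody dies, and it is at least as high as the proportion who actually have the event by that time.

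The component curves are where a reader looks to see which outcomes drive a composite that mixes death, a laboratory score, decompensation and a biopsy finding. If they are read as incidence, the non-fatal components look somewhat more frequent than they are. If mortality differs between arms, the distortion differs between arms too.

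A second gap sits underneath. With no last-contact date defined for deaths, two programmers could follow the SAP and draw different curves.

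**Working it through.** The documents give no component incidence, so there is no planned figure to reproduce. They also give no death rate. The check compares two quantities under constant, independent hazards.

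**Formulas.** Let h be the component rate, d the death rate and t the time in years.
- One minus Kaplan-Meier, death censored: 1 − exp(−h·t)
- Cumulative incidence, death competing: h/(h+d) × (1 − exp(−(h+d)·t))

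**Inputs.** Assumed: h of 1 or 3 per 100 person-years and d of 1% or 2% per year. From Protocol Section 7.1: t of 4 years (expected minimum follow-up) and 10 years (projected total study duration).

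**Example.** For h = 0.01, d = 0.01, t = 10: 1 − exp(−0.10) = 9.52%, against 0.5 × (1 − exp(−0.20)) = 9.06%. The difference is 0.45 points.

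| h | d | 1−KM, 4 y | CIF, 4 y | Excess | 1−KM, 10 y | CIF, 10 y | Excess |
|---|---|---|---|---|---|---|---|
| 0.01 | 0.01 | 3.92% | 3.84% | 0.08 | 9.52% | 9.06% | 0.45 |
| 0.01 | 0.02 | 3.92% | 3.77% | 0.15 | 9.52% | 8.64% | 0.88 |
| 0.03 | 0.01 | 11.31% | 11.09% | 0.22 | 25.92% | 24.73% | 1.19 |
| 0.03 | 0.02 | 11.31% | 10.88% | 0.43 | 25.92% | 23.61% | 2.31 |

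Excess is in percentage points.

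**Anchor from the documents.** Protocol Section 5.1 cites 21% to 26% of patients developing cirrhosis in 8.2 years. As a constant hazard, −ln(1−0.21)/8.2 = 0.0287 and −ln(1−0.26)/8.2 = 0.0367 per year. With h = 0.0287 at 10 years, one minus Kaplan-Meier is 25.0%, against a cumulative incidence of 23.8% (d = 1%) or 22.8% (d = 2%). Widening d to 0.25% to 3% and using both cirrhosis figures, the 10-year excess runs from 0.3 to 3.9 points.

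**Does the missing rule for deaths matter?** A simulation of 200,000 subjects (h = 0.0287, d = 0.01, administrative censoring uniform over 4 to 10 years) gives, at 8.2 years:
- death censored at death: 21.0%
- deceased subjects kept at risk to the data cutoff: 20.2%
- true cumulative incidence: 20.2%

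The bias therefore depends on a date that the last-contact rule does not define.

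**The case against.** The strongest reply is that the SAP never presents one minus Kaplan-Meier as an incidence. It promises curves and medians of time to event, and its incidence summaries carry exact binomial intervals, which belong to crude proportions. A reader might infer that the plan's component percentages will all be inflated. The documents do not support that: a crude proportion does not depend on how deaths are censored. This part of the reply stands.

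It does not make the curves harmless. The protocol plans about 291 composite events among stage 2 or 3 subjects on placebo and OCA 25 mg. With 2085 such subjects allocated 1:1:1, those two arms hold 2085 × 2/3 = 1390, and 291/1390 = 20.9%. That is for the whole composite, so single-component medians will very probably not be reached, and the curve becomes the main time-based display. The crude proportions ignore follow-up that varies from about 4 years upward.

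Three further points stand:
- Censoring at death is implied by Table 1 but not written.
- Ten years is the projected length of the study. A reader might take it as each subject's follow-up, but the expected minimum is about 4 years.
- Kaplan-Meier with deaths censored relates to the cause-specific hazard, which is a legitimate quantity. The difficulty arises when the curve is read as a risk.

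Finally, the text of SAP Section 6.2.3 on sensitivity analyses is not in the supplied document. The absence of a competing-risk method can be stated only for the visible text.

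**Conclusion.** The point holds as a low-severity improvement to a descriptive display. Kaplan-Meier is the only time-to-event estimator visible for the non-fatal components, death as a competing event is not addressed, and the last-contact rule omits deaths. If deaths are censored at death, the curves read as incidence are too high by about 0.1 to 0.4 points at 4 years and 0.5 to 2.3 points at 10 years. In relative terms that is about 2% to 4% and 5% to 10%. These sizes rest on assumed component and death rates and on constant, independent hazards. The direction does not depend on the rates chosen.

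A reader might infer that the main efficacy result is at risk. It is not: the primary composite counts all-cause death as an event, so death does not compete with it, and the visible text of Section 6.4.7.1 states no test for the components. Nor do the documents show that the distortion will differ between arms. That would require a mortality difference, which is unknown.

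**What to change.** In SAP Section 6.4.7.1, for each non-fatal component, report Aalen-Johansen cumulative incidence curves by arm with confidence intervals and with death as the competing event. State how liver transplant is treated for later liver events, since it can preclude or alter them. Keep Kaplan-Meier for all-cause death and for the composite. In the last-contact rule of SAP Appendix A, add a category for subjects who die, so that the date used is fixed before unblinding.

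The cost is a few sentences of SAP text and a small amount of extra programming with a standard procedure. No new data are needed, and alpha and the event target do not change. The plotted component percentages will be slightly lower than from Kaplan-Meier with deaths censored.
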